#### 8.1.2. Hematological Response

Hemoglobin and RBC transfusions will be primarily used to assess hematological response. Additionally, LDH and absolute reticulocyte count (ARC) will be used to distinguish between complete and major response (Table 5). Hematological response will be determined and summarized using counts and percentages by treatment category and study visit at 6-month intervals (i.e. Weeks 24, 48, 72, 96, 120, and 144). Bar charts of response by treatment category and time point will be produced.

Response	RBC Transfusions	Hemoglobin	LDH x ULN	ARC (/uL) a
Category		$(g/dL)^{a}$	а	
Complete response	None	≥12	≤1.5	≤ 150,000
Major response	None	$\geq$ 12	>1.5	Or >150,000
Good response	None	$\geq$ 10 and <12		
Partial response	$\leq$ 2 every 6 months	$\geq$ 8 and <10		
Minor response	$\leq$ 2 every 6 months	< 8		
Minor response	3 to 6 every 6 months,	< 10		
	or reduction of $\geq 50\%$ b			
No response	> 6 every 6 months and not reduction $\geq$ 50% b	< 10		

Table 5:Hematological Response Categories

ARC = absolute reticulocyte count; LDH = lactate dehydrogenase; RBC = red blood cell; ULN = upper limit of normal

a Hemoglobin, LDH, and ARC values should be median over 6-month period.

b 50% reduction compared with at least 6 months pre-study data.

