12.2. Blood Transfusions Review

At screening, the number of blood transfusions since the end of the prior trial will be recorded. During the trial, all blood transfusions will be documented, including the number of units and the blood product administered.

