14.3.7.1. Hematological Response Categories

Hematological response will be assessed every 6 months according to the criteria proposed by Risitano and colleagues (Risitano, Marotta, et al. 2019). Hemoglobin and RBC transfusions will be primarily used to assess response. Additionally, LDH and absolute reticulocyte count (ARC) will be used to distinguish between complete and major response (Table 7):

Table 7: Hematological Response Categories

Response Category	RBC Transfusions	Hemoglobin (g/dL) ^a	LDH \times ULN ^a	ARC (μ L) ^a
Complete response	None	≥ 12	≤ 1.5	$\leq 150,000$
Major response	None	≥ 12	> 1.5	Or $> 150,000$

Response Category	RBC Transfusions	Hemoglobin (g/dL) ^a	LDH × ULN ^a	ARC (/μL) ^a
Good Response	None	≥ 10 and < 12		
Partial response	≤ 2 every 6 months	≥ 8 and < 10		
Minor response	≤ 2 every 6 months	< 8		
	3 to 6 every 6 months, or reduction of ≥ 50% ^b	< 10		
No response	> 6 every 6 months	< 10		

Abbreviations: ARC = absolute reticulocyte count; LDH = lactate dehydrogenase; RBC = red blood cell; ULN = upper limit of normal

^a Hemoglobin, LDH, and ARC values should be median over 6-month period

^b 50% reduction compared with at least 6 months pre-study data

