## 5.2. General Post Text Summary Table and Individual Subject Data Listing Format Considerations

Tables and listings will be numbered to reflect main levels of unique tables and listings and sub-levels of replicate tables and listings with two digits per level (eg, Table XX.YY.ZZ....).

- 1. The first level number should be consistent with the corresponding Clinical Study Report (CSR) appendix in which the tables or listings will appear. Following ICH-E3, all post text tables should have first level 14 and data listings should have 16.2.
- 2. For tabular presentations, subject accounting and final disposition, baseline, and demographic profile should appear as the first sub-level (Table 14.1 series). Efficacy should come next (Table 14.2 series), followed by safety, PK/PD, and other special-purpose sections. Similar conventions should be applied to the subject data listings (16.2.1 for discontinuation, 16.2.2 for protocol deviations, and so on).

The title should be complete, accurate, and concise. If convenient, the parameter and unit of measurement can appear in parentheses to conserve space in the body of the table. For example, a summary of orthostatic vital signs title could read "Summary of Sitting and Standing Blood Pressure (SBP) (mmHg) and Heart Rate (HR) (bpm)." Whether in the title or body of a table or listing, units must always be specified for all appropriate data. The last line of the title should provide the analysis group being summarized (eg, Intent-to-Treat Population or Per-Protocol Population).

In general, variables summarized and statistics reported should appear in the left-most column of a table. The columns for treatment groups should report the data from left to right for each treatment group (see Section 7), and (optional) all treated subjects, respectively. Any row with all zeros will not appear except

with reasons for disposition events or other similar lists of results (e.g. categorical urinalysis results). Summary tables clearly indicate the number of subjects to which the data apply, and unknown or not performed are distinguished from missing data.

In general, the listings should be sorted and presented by treatment group, subject number, parameter (where applicable), and date/time.

All tables and listings must have explanatory notes that give the definition of all derived variables and decodes for coded data. Footnotes will be in past tense for ease of incorporation into in-text tables in the CSR.

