## 5.4. Data Presentation Conventions

Continuous data will be summarized using the number of subjects with available data, mean, standard deviation (SD), standard error of the mean (SE), median, and minimum and maximum. Categorical data will be summarized using counts and percentages. Percentages are calculated using the total number of subjects per treatment group unless otherwise specified.

Unless otherwise specified, means and medians are formatted to one more decimal place than the measured value, SDs, SEs, confidence interval (CI) limits, and coefficient of variation (CV) to two more decimal places, and minimum and maximum values to the same number of decimal places. For categorical variables, the number and percentage of responses will be presented in the form XX (XX.X%) where the percentage is in the parentheses, except that 100% will be presented to three digits with no decimal. Dates will be formatted DDMMMYYYY and times will be formatted in 24-hour time as HH:MM. Partial dates will be handled as described in Sections 5.7.10 and 5.7.11. P-values and CIs will use a two-sided 0.05 significance level unless otherwise noted; p-values will be presented with three decimal places. Extreme p-values or CIs will be presented as "<0.001" and ">0.999" with the appropriate number of places.

All BCX9930 concentrations will be reported as provided by the concentration vendor.

Wherever possible, data will be decimal aligned.

CONFIDENTIAL

A table of contents at the end of this SAP provides the expected titles and numbers of the tables, listings, and figures of the final report. Changes to titles or numbering in the final report will not necessitate a revision to the SAP, nor will it be considered a deviation from planned analyses. Additional data listings supporting the tables will not be considered a deviation from planned analyses.

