## 5.12. Data Handling Conventions

#### 5.12.1. Premature Withdrawal and Missing Data

No missing data will be imputed, except dates and times as mentioned above.

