#### **10.1.2.** Clinical Measurements of PNH

Continuous clinical measurements of PNH (LDH, hemoglobin, haptoglobin levels, absolute reticulocyte count, AST, total bilirubin, and direct bilirubin) will be summarized by summary statistics including change from baseline and percent change from baseline, by treatment category and study visit. Note that LDH, hemoglobin, haptoglobin, and absolute reticulocyte count that occur within a transfusion-impacted period will not be included in summaries but will be presented in respective listings. Categorical clinical measurements of PNH (number of blood transfusions, incidence of major thromboses) will be summarized with counts and percentages by treatment category (see Section 12.3 for a list of thrombosis events). Incidence of breakthrough hemolysis will be analyzed by the sponsor.

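### SAP Table 5 has no response category for a transfused subject with 6-month median hemoglobin of 10 g/dL or more, and the transfusion-handling rules around it need reconciling

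*SAP*

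**What the plan says.** **Response categories.** SAP 8.1.2 states "Hemoglobin and RBC transfusions will be primarily used to assess hematological response"; LDH and absolute reticulocyte count (ARC) only separate Complete from Major. Protocol 14.3.7.1 says the same: "Hemoglobin and RBC transfusions will be primarily used to assess response". Hb is the median over a 6-month period (footnote a of both tables). The SAP's No response row reads "> 6 every 6 months and not reduction" of at least 50%, with Hb below 10. The clause on reduction is absent from that row of protocol Table 7. Neither document gives a residual category.

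**Reporting rules.** SAP 5.4: "Percentages are calculated using the total number of subjects per treatment group unless otherwise specified". SAP 5.2: "Summary tables clearly indicate the number of subjects to which the data apply, and unknown or not performed are distinguished from missing data". SAP 5.12.1: "No missing data will be imputed, except dates and times as mentioned above".

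**Transfusion-impacted values.** SAP 5.7.13 defines a 14-day period (3 days for haptoglobin), lists the affected parameters without LDH, and limits the periods to effectiveness endpoints. Its subsections replace an impacted visit value with a qualifying pre-transfusion value and set it to missing only if none exists. SAP 10.1.2 says: "Note that LDH, hemoglobin, haptoglobin, and absolute reticulocyte count that occur within a transfusion-impacted period will not be included in summaries". SAP 9.2, in the safety section, adopts the 5.7.13 rules. SAP 5.6 filters baseline for transfusion for Hb, reticulocytes, PNH RBC, the RBC-to-WBC ratio, haptoglobin and FACIT-Fatigue, but not LDH.

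**The concern.** Hematological response is a named effectiveness endpoint with its own table (14.2.2.1) and bar charts. A fully observed subject who fits no row stays in the denominator under SAP 5.4 but appears in no category, so the categories do not add to 100%. Nothing in the SAP text separates that subject from one with missing data, although 5.2 promises such a distinction. Without a rule, someone has to decide after seeing open-label data.

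The transfusion rules matter for a related reason. Hb appears in Table 14.2.1 (durability) and again in Table 14.4.1.3 (clinical measurements), both effectiveness tables on the mITT population. If one substitutes and the other drops, the same Hb at the same visit has two values of n and two means. For LDH, post-baseline values filtered for transfusion would be compared with an unfiltered baseline.

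**Working it through.** **Step 1: is Table 5 exhaustive?** Inputs are the cut-points of SAP Table 5. I crossed four transfusion bands with four bands of median Hb (g/dL).

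| RBC transfusions in 6 months | Hb <8 | Hb 8 to <10 | Hb 10 to <12 | Hb ≥12 |
|---|---|---|---|---|
| 0 | Minor | Partial* | Good | Complete or Major |
| 1–2 | Minor | Partial* | **none** | **none** |
| 3–6 | Minor | Minor | **none** | **none** |
| >6 | No response† | No response† | **none** | **none** |

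\* Also meets the second Minor row if transfusions fell by ≥50%. † Minor if they fell by ≥50%.

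Empty cells: 3 transfusion bands × 2 Hb bands = 6 of 4 × 4 = 16. Splitting each cell by reduction (yes/no) gives 12 of 32, whatever the LDH or ARC. The 50% alternative does not close the gap, because that row also requires Hb below 10. Protocol Table 7 has the same empty cells.

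**Step 2: can a subject reach an empty cell?** Assume one Hb per scheduled visit and six 4-weekly visits (Days 29, 57, 85, 113, 141, 169). A 14-day window holds at most one visit, so one or two transfusions affect at most 2 of 6 values. The median of six is the mean of the 3rd and 4th smallest. If the other four or more values are ≥10, at most two values lie below 10, so the 3rd smallest is ≥10 and so is the median. This holds if the impacted values are kept, dropped or replaced by any low pre-transfusion value. The subject is unclassified in every case.

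**Step 3: more than six transfusions.** Take seven at intervals of 7 days or less. First to last is at most 6 × 7 = 42 days, and the windows cover at most 42 + 14 = 56 days. On nominal visit days 28 days apart, that is at most 56/28 = 2 visits. By step 2, if the other values are ≥10 the subject is unclassified instead of No response.

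**Step 4: does the handling rule matter to the median?** The SAP does not say which values feed it. In a hypothetical subject, visit Hb is 10.4, 10.2, 10.6, 9.0, 10.1 and 9.8; the 10.6 falls in a window and the pre-transfusion value is 7.9.

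- All values kept: (10.1 + 10.2)/2 = 10.15
- Impacted value dropped: middle of 9.0, 9.8, 10.1, 10.2, 10.4 = 10.10
- Impacted value substituted: (9.8 + 10.1)/2 = 9.95

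With 1–2 transfusions and no 50% reduction, this subject is unclassified under the first two and Partial under the third.

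**Step 5: Hb in Tables 14.2.1 and 14.4.1.3.** Suppose 10.1.2 drops values and 5.7.13 substitutes them. Let s be the share of subjects in a window at a visit, A the mean Hb of the others and P the mean pre-transfusion Hb. Exclusion gives A. Substitution gives (1 − s)A + sP. The difference is s(A − P). Shares and gaps below are assumptions.

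| Gap A − P (g/dL) | s = 5% | s = 10% | s = 20% |
|---|---|---|---|
| 0 | 0 | 0 | 0 |
| 1.5 | 0.075 | 0.15 | 0.30 |
| 3.5 | 0.175 | 0.35 | 0.70 |

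**Step 6: parameter lists.** Of the four parameters named in 10.1.2 (LDH, Hb, haptoglobin, ARC), only LDH is missing from both the 5.7.13 list and the 5.6 baseline filter.

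**The case against.** *The criteria are published.* That explains the gap but does not oblige the SAP to keep it. The SAP has already changed the No response row relative to the protocol, and it describes the criteria as modified for duration and visits. That description does not clearly cover a new category, so an added row must be declared.

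*10.1.2 and 5.7.13 can run in sequence.* A reader might infer a flat contradiction. The documents do not support that: 10.1.2 removes values inside an impacted period, and a 5.7.13 substitute lies outside one by definition. On that reading the two Hb tables agree and the differences in step 5 are zero. What stands is an ambiguity. 10.1.2 mentions neither replacement nor 5.7.13, and its wording resembles the FACIT-Fatigue rule, where values are dropped with no substitute.

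*LDH exclusion is programmable.* True. 5.7.13 sets 14 days generally, with haptoglobin the only exception. The mismatch with the list and the baseline remains.

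*Heavily transfused subjects.* A reader might infer that evenly spaced transfusions also escape No response. That does not follow. Seven in 168 days are 24 days apart, so the only days outside a window are days 14–23 after each transfusion. Scheduled values and substitutes both come from that stretch, so one cannot be assumed high and the other low. The escape is shown only for clustered transfusions.

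*A residual row may exist.* Display specifications are in a separate document, so this cannot be ruled out. The category rule itself still belongs in the SAP.

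**Conclusion.** The response table is wrong as written: 6 of 16 cells have no category, and no rule in either document fills them. For one or two transfusions on 4-weekly visits the gap is reached whenever Hb at the unaffected visits is ≥10. This rests on one Hb per scheduled visit, but not on how impacted values are handled. For more than six transfusions it is shown for clusters on nominal visit days.

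The number of subjects affected cannot be computed from the documents. A reader might infer that the gap flatters the drug; the documents do not support a net direction. Some unclassified subjects would otherwise be No response, but most would otherwise be Partial or Minor. No direction of LDH bias is claimed either.

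The 10.1.2 wording is an ambiguity, with the Hb differences above arising only on its literal reading. The LDH mismatch and the conflict between 9.2 and the 5.7.13 limit are plain in the text. Response category is an effectiveness endpoint, not a listed secondary endpoint; the primary endpoint is safety and there is no control group. The weight lies between minor and should-fix.

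**What to change.** Before database lock:

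1. Make Table 5 exhaustive and mutually exclusive. More than six transfusions without a ≥50% reduction is No response at any Hb. Every other subject with at least one transfusion and median Hb ≥10 goes to a separately reported row (transfused, median Hb ≥10), kept in the denominator and not counted as Complete, Major or Good. Where Partial and Minor both match, assign Partial. Declare these as modifications of the published criteria.
2. State that the Table 5 median uses values handled under 5.7.13. Define the pre-study period in footnote b. Say whether transfusions are counted as episodes or units; both are available, since protocol 12.2 says "During the trial, all blood transfusions will be documented, including the number of units and the blood product administered".
3. In 10.1.2, replace the exclusion wording with a cross-reference to 5.7.13.
4. Treat LDH the same way in 5.6, 5.7.13 and 10.1.2: listed in all or filtered in none. Reconcile 9.2 with the 5.7.13 limit to effectiveness endpoints.

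The cost is table and wording edits and minor reprogramming, with no new data. The small downside is a declared departure from the published response criteria.

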## 8.1.3. Patient Reported Outcomes

#### 8.1.3.1. Treatment Satisfaction Questionnaire for Medication

The TSQM questionnaire will be completed at Baseline and at the Week 12, 24, 48, 72, and 96 visits. The individual question data from the TSQM will be listed. Domain scores will not be calculated.

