6.4. Secondary Endpoints

- Clinical PNH symptom assessments including fatigue, dyspnea, chest pain/discomfort, difficulty swallowing (esophageal pain), abdominal pain, headache, erectile dysfunction, hemoglobinuria, jaundice, incidence of BTH, and incidence of thromboembolic events.
- Clinical measurements of PNH (LDH, hemoglobin, haptoglobin, reticulocytes, transfusion requirements).
- PRO endpoints will include scores from the Quality of Life Questionnaire for Patients with Aplastic Anemia/PNH (QLQ-AA/PNH), Functional Assessment of Chronic Illness Therapy (FACIT) fatigue scale, and Treatment Satisfaction Questionnaire for Medication (TSQM).
- Concentration of BCX9930 in plasma at steady state in subjects with PNH.

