#### Patient Reported Outcomes:

Questionnaires will be used to evaluate quality of life (QLQ-AA/PNH), effectiveness of therapy (FACIT fatigue scale) and treatment satisfaction (TSQM).

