#### **3.2.2.** Secondary Endpoints

- Clinical PNH symptom assessments including fatigue, dyspnea, chest pain/discomfort, difficulty swallowing (esophageal pain), abdominal pain, headache, erectile dysfunction, hemoglobinuria, jaundice, incidence of BTH, and incidence of thromboembolic events.
- Clinical measurements of PNH (LDH, hemoglobin, haptoglobin, reticulocytes, transfusion requirements).
- PRO endpoints will include scores from the Quality of Life Questionnaire for patients with Aplastic Anemia / Paroxysmal Nocturnal Hemoglobinuria (QLQ-AA/PNH), Functional Assessment of Chronic Illness Therapy (FACIT) fatigue scale, and Treatment Satisfaction Questionnaire for Medication (TSQM).
- Concentration of BCX9930 in plasma at steady state in subjects with PNH.

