## 8. EFFECTIVENESS

The following effectiveness endpoints will be summarized and listed:

- Durability of response
- Hematological response (categorization of response according to criteria in Table 5)
- PROs: QLQ-AA/PNH, FACIT fatigue scale, TSQM scores
- Clinical measurements of PNH (LDH, hemoglobin, haptoglobin, reticulocytes, transfusions)
- Subjects with dose escalation
- Discontinuations due to lack of efficacy
- Disease severity as recorded by the PNH symptoms assessment

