#### CONFIDENTIAL

#### 8.1.3.2. Quality of Life Questionnaire for Patients with Aplastic Anemia/PNH

The QLQ-AA/PNH will be completed at Baseline and at the Week 24, 48, 72, and 96 visits. It has 54 items in 12 domains: body image (BI), cognitive functioning (CF), emotional functioning (EF), fatigue (FA), illness intrusiveness (II), fear of progression (PAF), infections (IN), other symptoms (OS), physical functioning (PF), role functioning (RF), social support (SS), and stigmatization (ST). The individual question data from the QLQ-AA/PNH will be listed. Domain scores will not be calculated.

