## 8.1.4.3. Discontinuation Due to Lack of Efficacy

Discontinuation due to lack of efficacy was not captured in the eCRF and so cannot be summarized specifically. Captured discontinuation reasons will be summarized on the disposition table.

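### QLQ-AA/PNH and TSQM scores are a secondary endpoint due a summary, but the SAP lists item responses only, scores neither instrument and plans no table or figure for either

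*SAP*

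**What the plan says.** **The commitment.** SAP 3.2.2 states: "PRO endpoints will include scores from the Quality of Life Questionnaire for patients with Aplastic Anemia". The same sentence goes on to name FACIT-Fatigue and the TSQM. Protocol 6.4 and the synopses of both documents define the endpoint in the same way. SAP section 8 opens its list of endpoints with "The following effectiveness endpoints will be summarized and listed", and one entry is "PROs: QLQ-AA/PNH, FACIT fatigue scale, TSQM scores". Protocol 14.3.7 carries the same commitment and leaves the detail to the SAP.

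**The instrument rules.** For the TSQM, SAP 8.1.3.1 says: "The individual question data from the TSQM will be listed. Domain scores will not be calculated". For the QLQ-AA/PNH, SAP 8.1.3.2 describes 54 items in 12 domains and then says: "The individual question data from the QLQ-AA/PNH will be listed. Domain scores will not be calculated". FACIT-Fatigue is treated differently. It has a total score (SAP 8.1.3.3), an algorithm with a missing-item rule (SAP 12.4), and a planned summary of score and change from baseline.

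**The planned output.** In SAP 12.1, Table 7, the only table for a patient-reported outcome is 14.2.3, for FACIT-Fatigue. The QLQ-AA/PNH and the TSQM appear only as item listings, 16.2.7 and 16.2.9.

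**The concern.** The endpoint is a score and the plan promises to summarise it. The detailed rules then remove the score and put nothing in its place. A listing of individual answers is not an estimate of anything, whereas SAP 3.3 says that estimation is the emphasis of this uncontrolled study.

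The instruments are not interchangeable. The SAP synopsis assigns quality of life to the QLQ-AA/PNH, treatment satisfaction to the TSQM and effectiveness of therapy to FACIT-Fatigue. If the SAP is followed, the report will have no summary of treatment satisfaction from any source. It will also have none for the disease-specific domains named in SAP 8.1.3.2, such as body image, stigmatization and fear of progression. Scoring done after the data are in would have no prespecified algorithm and no missing-item rule.

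**Working it through.** No statistical figure is involved, so the check compares texts and counts planned displays.

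**1. Commitment against output, by instrument**

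| Instrument | Score is an endpoint (SAP 3.2.2) | Summary promised (SAP 8) | Score derived | Table or figure in Table 7 | Listings in Table 7 |
|---|---|---|---|---|---|
| FACIT-Fatigue | yes | yes | yes (8.1.3.3, 12.4) | 14.2.3 | 16.2.8.1, 16.2.8.2 |
| QLQ-AA/PNH | yes | yes | no (8.1.3.2) | none | 16.2.7 |
| TSQM | yes | yes | no (8.1.3.1) | none | 16.2.9 |

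**2. Counts from Table 7**
- Displays for patient-reported outcomes: 1 table + 4 listings = 5. No figure covers any of the three instruments.
- Displays that contain a score: 14.2.3 and 16.2.8.2 = 2, both FACIT-Fatigue.
- Instruments without any summary: 2 of 3. QLQ-AA/PNH domains scored: 0 of 12.

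**3. Planned assessments left without a summary**
- QLQ-AA/PNH after baseline: Weeks 24, 48, 72 and 96 = 4.
- TSQM after baseline: Weeks 12, 24, 48, 72 and 96 = 5.
- Sum: 4 + 5 = 9 instrument-visits. These fall on 5 distinct weeks.
- For scale: 54 items × 5 time points (baseline plus 4) = 270 QLQ-AA/PNH answers per subject. With about 200 subjects, 270 × 200 = 54,000 listed values and no planned aggregate. This is an upper bound that assumes full enrolment and complete data.

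**4. Can the passages be reconciled?**
- *A score by another route.* Neither subsection specifies a total score or an item-level summary, so without domain scores there is no score.
- *Tables added later.* SAP 5.4 and 12.1 allow changes to titles and numbering and extra supporting listings. SAP 12.1 also allows displays to be split. Neither covers new summary tables.
- *Deviation reporting.* Protocol 14.3 has deviations from the SAP described in the study report. The SAP says both things, so it is unclear whether leaving out the summary would count as one.
- *A stated reason.* For another section 8 endpoint that cannot be delivered, SAP 8.1.4.3 explains why: "Discontinuation due to lack of efficacy was not captured in the eCRF and so cannot be summarized specifically". The readable SAP text has no such statement for these two instruments.

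**The case against.** The strongest reply is that the working instruction is clear. Protocol 14.3.7 delegates the detail to the SAP, the two subsections are explicit, and Table 7 agrees with them. A programmer would know what to produce, and the opening of section 8 may simply be text carried over from the protocol. This stands as far as programming goes. It does not remove the conflict with SAP 3.2.2, the SAP synopsis and Protocol 14.3.7, all of which still treat the scores as an endpoint.

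A second reply is that the documents promise summarised scores, but not domain scores or change from baseline for these instruments. That is correct. The defect is the missing summary; domain scoring and change from baseline are the proposed remedy. Change also needs care. SAP 5.6 generally takes the Day 1 value as baseline, Protocol 7.1 uses the final on-treatment visit of the prior study for direct rollovers, and Protocol 14.3.2 refers to the baseline value reported in the prior study. For direct rollovers, change may therefore run from one treated state to another, in subjects selected for benefit.

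Third, the front pages of the SAP were not available to this review, and SAP 12.2 puts display specifications in a separate document. A reason may be given there. It would explain the choice but would not reconcile section 8 with its own subsections.

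Two stronger readings are tempting:
- A reader might infer that the questionnaire data are lost or that results are being withheld. The documents do not support this: every item response is collected and listed, and nothing in the text indicates a motive.
- A reader might also see one pattern with breakthrough hemolysis (Protocol 14.3.6 against SAP 10.1.2) and drug concentrations (Protocol 14.3.9 and the SAP synopsis against SAP 11.1). Those are mainly deferrals. The protocol already defines breakthrough hemolysis and its outputs, and the SAP assigns its incidence to the sponsor. PK analysis goes to a separate plan. They are minor cross-reference points and not part of this one.

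**Conclusion.** The point holds. The SAP contradicts itself and the protocol: a secondary endpoint that is to be summarised gets a listing of answers for two of its three instruments, and the readable text gives no reason. The secondary objective on patient-reported outcomes (SAP 3.1.2) then rests on FACIT-Fatigue alone.

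The consequence is limited. The primary endpoint is safety, no hypothesis test depends on these scores, and the item data can still be scored. It should be corrected before the final analysis, but it does not threaten the study's main conclusions. The conclusion assumes that Table 7 is the full list of planned tables and figures, as SAP 12.1 presents it apart from the changes allowed there, and that no unseen document supplies the missing summaries.

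**What to change.** **Preferred change.** In SAP 8.1.3.1 and 8.1.3.2, replace the statement that domain scores will not be calculated with scoring by each instrument's published rules. The sponsor should cite those rules and include a missing-item rule; the documents give an algorithm for FACIT-Fatigue only. Add to Table 7, for the mITT population, tables of score and change from baseline by treatment category and visit, as for FACIT-Fatigue. State which baseline applies to subjects who roll over directly.

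**If no usable scoring rule is available.** Summarise item responses by visit as counts and percentages, and give the reason, as SAP 8.1.4.3 does for its endpoint. Align the SAP synopsis, 3.2.2 and section 8, and record the departure from Protocol 14.3.7. Rewording section 8 alone is not enough: it adds no result and leaves the synopsis and 3.2.2 naming scores that nobody will calculate.

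**Cost.** SAP wording, a few extra tables and some scoring work. The scoring effort depends on instrument manuals that are not in the documents. No new data and no change to study conduct are needed.
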